LDL Low Density Lipoprotein (cholesterol)

METC Medical research ethics committee (MREC); in Dutch: medisch ethische toetsing

commissie (METC)

PISA Periodontal Inflamed Surface Area

PPZ Practice for Periodontology Zwolle (Dutch: Praktijk voor Parodontologie Zwolle)

(S)AE (Serious) Adverse Event

Sponsor The sponsor is the party that commissions the organisation or performance of the

research, for example a pharmaceutical

company, academic hospital, scientific organisation or investigator. A party that provides funding for a study but does not commission it is not regarded as the

sponsor, but referred to as a subsidising party.

SUSAR Suspected Unexpected Serious Adverse Reaction

Wbp Personal Data Protection Act (in Dutch: Wet Bescherming Persoonsgevens)
WMO Medical Research Involving Human Subjects Act (in Dutch: Wet Medisch-

wetenschappelijk Onderzoek met Mensen

WHR Waist to Hip Ratio

SUMMARY

Rationale:

Periodontitis is a chronic multi-causal inflammatory disease of the supportive tissues of the teeth with progressive loss of attachment and alveolar bone. Atherosclerosis is perceived today as a chronic inflammatory condition, and infectious diseases are believed to contribute to its pathophysiology. In recent years remarkable pathological and epidemiological relationships between periodontitis and atherosclerosis have been presented. Many previous studies use surrogate biomarkers in order to demonstrate the association between periodontitis and atherosclerosis. Unfortunately, more definitive cardiovascular parameters and endpoints are still lacking.

Objective:

The aim of this study is to determine if there is an association between the PISA score and the coronary calcium score. In other words, whether the presence and the extent of periodontitis is related to the presence and extent of coronary calcification as seen on the coronary calcium score..

Study design:

Cross-sectional pilot study

Study population:

50 human volunteers without known systemically diseases, 45-70 years old, who visited the Practice for Periodontology Zwolle (PPZ) for either recently diagnosed periodontitis or dental implants.

Main study parameters/endpoints:

All patients have to fill in questionnaires to gather data on their medical history, perceived health, parental history, lifestyle, socio-economic status and oral hygiene. A physical examination (Blood Pressure (BP), Heart Rate (HR), Body Mass Index (BMI), Waist to Hip ratio (WHR), Electrocardiogram (ECG)), a periodontal index, a standard dental panoramic radiograph, oral microbiological samples and blood test (hsCRP, total cholesterol, HDL-cholesterol, triglycerides, eGFR, HbA1c, genotyping) will be obtained. Inflammatory burden of periodontal disease will be quantified with the Periodontal Inflamed Surface Area (PISA) score. To acquire data about the cardiovascular condition, we will obtain a Coronary Calcium Score by a CT-scan. The endothelial function will be measured employing "EndoScore" using the ENDOPAT.

Nature and extent of the burden and risks associated with participation, benefit and group relatedness:

The radiation exposure of a standard dental panoramic radiograph is estimated to be 0.010 mSv, comparable to 1 day background exposure to the natural radiation in The Netherlands. The radiation exposure of a cardiac CT-scan for coronary calcium scoring is estimated to be 1.5 mSv for each participant. This is comparable to 6 months background exposure to the natural radiation in The Netherlands.

Version number: 2,27 March 2013 8 of 23

1. INTRODUCTION AND RATIONALE

Cardiovascular disease is the leading cause of death and morbidity in the Western world. The underlying pathology, atherosclerosis, is a progressive disease characterized by the accumulation of lipids and fibrous elements in the large arteries. It constitutes the most important contributor to the growing burden of cardiovascular disease. Over the past two decades, inflammation has emerged as an integrative factor for atherosclerosis. Inflammation can operate in all stages of this disease from initiation through progression and, ultimately, the thrombotic complications of atherosclerosis.

Periodontitis is a chronic multi-causal inflammatory disease of the supportive tissues of the teeth with progressive loss of attachment and alveolar bone. It is the most common oral disease, affecting 40-50% of the adults and approximately 10% of the population in its most severe form.³ The first study that found positive epidemiological evidence for the association between periodontitis and atherosclerosis was in 1989 by Mattila *et al.*⁴ Thereafter, in more recent years, remarkable pathological and epidemiological associations between these two diseases have been presented.⁵ A very important topic, with regard to the high incidence of both diseases, their economic costs to society and the potential impact on public health, is risk modification and identification of therapeutic opportunities.⁶

Biological mechanisms for the association between periodontitis and coronary heart disease

Several pathophysiological pathways have been suggested to explain the association between periodontitis and atherosclerosis. These pathways involve both direct and indirect mechanisms.

Indirect mechanism: Increased level of systemic inflammation: Periodontitis is associated with increased levels of C-reactive protein (CRP), fibrinogen, tumor necrosis factor-α, IL-1, IL-6, IL-8 and other acute phase reactants.⁷ These inflammatory reactants promote systemic inflammation and are associated with atherosclerosis. In case of systemic inflammation, endothelial cells stimulated by these inflammatory reactants increase their expression of various leukocyte adhesion molecules. Once adherent to the activated endothelial layer, the monocyte moves between the endothelial cells to penetrate into the innermost layer of the arterial wall and initiates an atherosclerotic lesion. Once resident in the arterial intima, monocytes acquire the morphological characteristics of macrophages, undergoing a series of changes that lead ultimately to foam cell formation. These foam cells are lipid-laden macrophages and characterize the early atherosclerotic lesion. Macrophages within atherosclerotic plaques also secrete a number of growth factors and cytokines involved in lesion progression and complication.²

Indirect mechanism: Increased platelet activation: Periodontitis is associated with increased p-selectin and platelet activation. P-selectin functions as a cell adhesion molecule on the surfaces of arterial endothelial cells and activates platelets, in response to inflammation. Periodontopathogens are able to directly cause activation of endothelial cells and platelets. Since platelet activation contributes to a pro-coagulant state and constitutes a risk for atherothrombosis, platelet activation in periodontitis may partly explain the epidemiological association between periodontitis and atherosclerosis.

Version number: 2,27 March 2013 9 of 23

Direct mechanism: Invasion of periodontal pathogens into atherosclerotic plaques: Bacteremia that originates from the mouth is a common event that occurs multiple times a day while chewing and tooth brushing, especially in patients suffering gingivitis and periodontitis. Periodontal pathogens (i.e. Porphyromonas gingivalis, Aggregatibacter *Actinomycetemcomitans*, Prevotella intermedia, Treponema denticola and Eikenella corrodens) enter the circulation via the gingival sulcus. These periodontal pathogens adhere to and invade in vascular endothelial cells. Infection of these endothelial cells by the periodontal pathogens (in particular Porphyromonas gingivalis) induces a procoagulant response that might contribute to formation of an atherosclerotic plaques. Moreover, periodontal pathogens have been found in atherosclerotic plaques.

Potential genetic mechanism: The recent identification of a shared genetic locus, ANRIL, for periodontitis and atherosclerosis/coronary heart disease, is a factor of unknown influence, but could be even more important than the above proposed biological mechanisms. ¹² The function of ANRIL and its role in periodontitis and atherosclerosis is still lacking.

Epidemiological evidence for the association between periodontitis and atherosclerosis

Several epidemiological studies have confirmed the association between periodontitis and atherosclerosis. The first study that found positive epidemiological evidence for this association was in 1989 by Mattila et al.⁴ Bahekar et al. recently summarized the subsequent studies in a systematic review revealing five prospective cohort studies (follow-up >6 years), five case-control studies and five cross-sectional studies. Meta-analysis of the five prospective cohort studies (86092 patients) indicated that individuals with periodontitis had a 1.14 times higher risk of developing coronary heart disease (CHD) than the controls (relative risk 1.14, 95% CI 1.074–1.213, *P* < 0.001). The case–control studies (1423 patients) showed an even greater risk of developing CHD (OR 2.22, 95% CI 1.59-3.117, P < 0.001). The prevalence of CHD in the cross-sectional studies (17724 patients) was significantly greater among individuals with periodontitis than in those without periodontitis (OR 1.59, 95% CI 1.329–1.907, P < 0.001). The individual studies were well be adjusted for confounding factors, because of the extensive documented impact of many prevalent risk factors, shared by periodontitis and CHD. These shared risk factors include increasing age, male sex, race/ethnicity, education and socio-economic status, stress, smoking, alcohol abuse, diabetes mellitus and overweight. 14, 15

Clinical evidence in the literature for the association between periodontitis and atherosclerosis

Observational studies using surrogate endpoints: Periodontitis can correctly be diagnosed and controlled by intra-oral examination (gingival bleeding, pocket-depth, loss of attachment and microbiological sampling or analysis) and dental X-ray (loss of alveolar bone). However, to strictly diagnose atherosclerosis, there is a need of invasive techniques such as angiography of the coronary arteries. Today, several surrogate biomarkers and imaging tools for atherosclerosis are in clinical and experimental use. Since inflammation has emerged as an integrative factor for atherosclerosis, epidemiological studies have found increased vascular risk in association with increased levels of inflammatory biomarkers such as cytokines (IL-6, TNF- α), cell adhesion molecules (P selectin) and acute-phase reactants (CRP, fibrinogen), which are elevated in periodontitis patients.⁷ Growing evidence indicates

Version number: 2 ,27 March 2013 10 of 23

that elevated circulating inflammatory markers, in particular CRP, are predictors for an unfavorable course, independent of the severity of the CHD or inflammatory burden. Paraskevas *et al.* showed in a meta-analysis of 10 cross-sectional studies that the weighted mean difference of CRP between periodontitis patients and controls was 1.56 mg/l (p < 0.00001). Elevated levels of CRP (>2.1 mg/l) are associated with a higher incidence of acute thrombotic events including stroke and myocardial infarction. CRP levels >2.1 mg/l in healthy individuals may be associated with a chronic pro-coagulant state and they may serve as markers for an increased long-term risk of CHD. 17

Besides, there are a number of other non-invasive surrogate subclinical markers of cardiovascular disease, focused on the endothelial function and arterial stiffness, including measurement of the carotid arteries, echocardiography, ankle-brachial index, flow-mediated dilation (FMD) in the brachial artery and pulse waveform analysis. Söder *et al.* found significantly higher mean values of the common carotid artery intima-media thickness (IMT) and calculated intima-media area (cIMA) in patients with periodontitis than in controls, both at the right (P < 0.01 and P < 0.001, respectively) and left side (P < 0.001 for both variables). Carotid IMT increase is associated with a raised risk of CHD. Endothelial dysfunction precedes clinical manifestation of atherosclerosis. Flow-mediated dilation (FMD) of the brachial artery assesses the endothelial function and is decreased in subjects with atherosclerosis. Amar *et al.* displayed that subjects with advanced periodontitis had lower FMD compared with control patients (7.8 + -4.6% versus 11.7 + -5.3%, P = 0.005).

Clinical trials concentrated on atherosclerotic risk reduction after periodontal treatment: Whether or not periodontal treatment reduces the risk for atherosclerosis or complications of atherosclerosis have not yet been established. The majority of the intervention trails, aimed to study this purpose, has examined the effect of periodontal treatment on markers of systemic inflammation or surrogate biomarkers of atherosclerosis. A recent meta-analysis on C-reactive protein in relation to periodontitis has indicated that periodontal treatment resulted in a weighted mean reduction in serum CRP of 0.5 mg/l (95% CI 0.08–0.93, p = 0.02). This reduction leads to clinical relevant improvements in systemic inflammation. Tonetti *et al.* sought to assess the effect on intensive periodontal treatment on endothelial function measured by FMD of the brachial artery. FMD was greater, and thus improved, in the intensive-treatment group than in the control-treatment group 60 days after therapy (absolute difference 0.9%; 95% CI, 0.1 to 1.7; P = 0.02) and 180 days after therapy (difference, 2.0%; 95% CI, 1.2 to 2.8; P < 0.001). The degree of improvement was associated with improvement in measures of periodontal disease.

Conclusion

The association between periodontitis and atherosclerosis is of great public health importance because of the high prevalence of both diseases and the potential impact on public health if risk modification or therapeutic opportunities could be identified. Previous studies use surrogate biomarkers in order to investigate the association between periodontitis and atherosclerosis. Unfortunately, more definitive cardiovascular parameters and endpoints are still lacking.

Several biological pathways have been suggested to explain this association; however, causal mechanisms are still not demonstrated. Polymorphisms in the ANRIL gene, which has been associated with both atherosclerosis and periodontitis, might be an important factor.

Several studies have evaluated the effects of periodontal treatment on endothelial function, in particular improvement of the cardiovascular condition through an increase of flow-mediated dilation (FMD) after periodontitis intervention has been observed. However, these

Pilot: The association between coronary atherosclerosis and periodontitis

studies utilize the brachial artery, which is a surrogate for the condition of coronary arteries. Besides, only subjects with severe periodontitis have been included in these clinical trials of periodontal therapy and endothelial function improvement. Therefore, there is still no available evidence that periodontal treatment improves endothelial function in subjects affected by the more prevalent forms, i.e. slight or moderate periodontitis. Studies exploring the effects of periodontal therapy in atherosclerotic patients with periodontitis are needed because treatment studies with periodontitis patients without atherosclerosis have shown benefits for cardiovascular system. We designed studies focused on more definitive quantification of the link between periodontitis and atherosclerosis, and the benefits of periodontal intervention in atherosclerotic patients. Further, the prevalence of ANRIL risk alleles will be linked with inter-individual variation in response to periodontal therapy. Finally in all participants microbiological samples will be taken for the determination of the oral microbiome using pyrosequencing, to determine a possible specific "fingerprint" of oral microbiome associated with atherosclerosis.

Relevance for science, technology or society

This study may provide clinical evidence that periodontitis is a risk indicator for atherosclerosis. In the future, patients suffering from periodontitis might be screened for atherosclerosis. Early diagnosis of atherosclerosis, coupled with secondary prevention such as life-style changes and targeted medication, has been shown to have a favourable effect on the course of the disease. Besides, diagnosed atherosclerotic patients if suffering from periodontitis are likely to benefit from periodontal treatment.

Version number: 2 ,27 March 2013 12 of 23

2. OBJECTIVES

The aim of this study is to determine if there is an association between the PISA score and the coronary calcium score. In other words, whether the presence and the extent of periodontitis is related to the presence and extent of coronary calcification as seen on the coronary calcium score..

3. STUDY DESIGN

This is a cross-sectional (pilot) study, coordinated by the department of Oral and Maxillofacial Surgery of the Academic Medical Center (AMC), and the Department of Periodontology, ACTA, Amsterdam. Patients from the Practice for Periodontology Zwolle will be recruited. The department of Cardiology from the Isala Clinics will obtain the physical examinations, blood test, arterial stiffness test and the Coronary Calcium Score (CCS).

4. STUDY POPULATION

4.1 Population (base)

Patients who visited the Practice for Periodontology Zwolle for either recently diagnosed periodontitis or dental implants.

4.2 Inclusion criteria

- Age 45-70 years
- Male and Female
- All ethnicities
- ≥ 10 teeth

4.3 Exclusion criteria

- Edentulous
- Known cardiovascular diseases
- Known Diabetes Mellitus
- Known autoimmune disorders
- Known immunosuppressive disorders

4.4 Sample size calculation

Not applicable. There is no data available on which a sample size calculation can be based. This is a pilot and feasibility study with 50 participants to determine the study population size needed for a full study.

5. TREATMENT OF SUBJECTS

Not applicable for this study.

6. INVESTIGATIONAL MEDICINAL PRODUCT

Not applicable for this study.

Version number: 2 ,27 March 2013 13 of 23

7. METHODS

7.1 Study parameters/endpoints

7.1.1 Main study parameter/endpoint

Periodontal Inflamed Surface Area (PISA): 23

Periodontal inflamed surface area (PISA) quantifies the amount of inflamed periodontal tissue in square centimetres and is supposed to quantify the inflammatory and infectious burden resulting from periodontitis. PISA will be calculated after extensive periodontal examination including periodontal probing pocket depth (PD), gingival recession, plaque score, and bleeding on probing (BOP) measurements by trained and calibrated examiners. All measurements will be performed on all teeth, on six sites per tooth using a manual periodontal standard probe. Clinical attachment loss (CAL) will be defined as the distance from the cementoenamel junction to the bottom of the pocket/sulcus and calculated as the mathematical sum of the PD and gingival recession measurements. Measurements will be made in millimeters and will be rounded off to the nearest millimeter. BOP will be recorded as either present or absent within 30 seconds of probing at six sites per tooth. Plaque score will be defined as being present or absent at six points on each tooth. The number of missing teeth will also be recorded.

Coronary Calcium Score (CCS): 24

Quantifying the amount of coronary artery calcium (CAC) with cardiac CT has been widely accepted as a reliable non-invasive technique for predicting risk of future cardiovascular events. Although CT-detected coronary calcification only allows evaluation of the calcified component of coronary plaques, a good correlation has been found between the Coronary Calcium Score and the total amount of coronary atherosclerosis as assessed by intravascular ultrasound and histology. Thus, the CCS is a good measure for the total amount of coronary atherosclerosis, including stable and vulnerable plaques. Interestingly, the CCS has been found to have a closer association with total coronary plaque burden compared with the presence of luminal stenosis. An increasing amount of coronary calcification is correlated with the probability of obstructive coronary artery disease by invasive coronary angiography.

Endothelial dysfunction (EndoScore): 25

Endothelial dysfunction has been recognized as the critical junction between risk factors and clinical disease. It is the earliest detectable stage of cardiovascular disease. EndoPAT is a medical device for noninvasive endothelial function assessment. EndoPAT is based on noninvasive Peripheral Arterial Tone (PAT) signal technology. It measures endotheliummediated changes in vascular tone using unique bio-sensors placed on the fingertips. These changes in arterial tone are elicited by creating a down-stream hyperemic response induced by a standard 5-minute occlusion of the feeding artery (using a standard blood pressure cuff). When the cuff is released, the surge of blood flow causes an endothelium-dependent Flow Mediated Dilatation (FMD). The dilatation, manifested as Reactive Hyperemia, is captured by EndoPAT as an increase in the PAT Signal amplitude. A post-occlusion to preocclusion ratio is automatically calculated by the EndoPAT software, thus providing the EndoScore. Measurements from the opposite arm are used to control for concurrent nonendothelial dependent changes in vascular tone. EndoPAT tests can be carried out in both the office and hospital settings, with patients positioned either sitting or supine. The test takes 15 minutes to complete, is very easy to perform, and is both operator and interpreter independent.

Version number: 2 ,27 March 2013 14 of 23

7.1.2 Secondary study parameters/endpoints

Reynolds risk score: 26

The Reynolds Risk Score is designed to predict the risk, in non-diabetic patients, of having a future heart attack, stroke, or other major cardiovascular event in the next 10 years. This model includes age, current smoking, parental history of a cardiovascular event, <age 60 years, blood pressure, hs-CRP and total and HDL cholesterol.

Framingham risk score: 27

The Framingham risk score is one of the most commonly used risk-estimation systems, which enables clinicians to estimate cardiovascular risk in asymptomatic patients. It is calculated using traditional risk predictors, including age, gender, total cholesterol, high-density lipoprotein cholesterol, smoking status, and systolic blood pressure, and is represented as a 10-year risk score for the prediction of coronary artery disease events.

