9. STATISTICAL ANALYSIS

Primary outcome is the correlation between the PISA score and the coronary calcium score. Therefore 2 groups of 25 patients will be analysed. One group diagnosed with periodontal disease and one group with a healthy periodontium. For description of the data the mean values, standard deviations, minimum and maximum are calculated. For continuous data, differences between the groups will be analysed using the independent T-test. If the data violates the assumption of a normal distribution, differences between the groups will be analysed using the Mann-Whitney test. Binary data will be assessed using the Pearson chi-square test. Correlation between the overall PISA score and the coronary calcium score will be calculated with the Spearman correlation test. Outcome variables that show significant between-groups differences at baseline will be used as covariate in a multivariate regression analysis. Data will be entered in a database (SPSS) and analyzed using SPSS statistical package 18.0 (SPSS Inc. Chicago, II

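### The Reynolds and Framingham scores share inputs with periodontitis, so a group difference in them is not evidence of coronary atherosclerosis; the PISA-calcium analysis needs a pre-specified Framingham adjustment instead

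*Protocol*

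**What the plan says.** Protocol section 7.1.2 lists the Reynolds and Framingham scores and nothing else. For Reynolds: "This model includes age, current smoking, parental history of a cardiovascular event, <age 60 years, blood pressure, hs-CRP and total and HDL cholesterol". For Framingham: "It is calculated using traditional risk predictors, including age, gender, total cholesterol, high-density lipoprotein cholesterol, smoking status, and systolic blood pressure"; the result "is represented as a 10-year risk score for the prediction of coronary artery disease events". The direct vascular measures, the coronary calcium score and the EndoScore, are in section 7.1.1.

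On confounding, section 1 states: "These shared risk factors include increasing age, male sex, race/ethnicity, education and socio-economic status, stress, smoking, alcohol abuse, diabetes mellitus and overweight". On CRP, it reports that in a meta-analysis of 10 cross-sectional studies the "weighted mean difference of CRP between periodontitis patients and controls was 1.56 mg/l". The same section presents systemic inflammation, CRP included, as one route from periodontitis to atherosclerosis.

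Section 9 defines the primary outcome as the correlation between PISA and the calcium score (Spearman) and describes two groups of 25, with and without periodontal disease. No matching is stated. The general rule for group comparisons is: "For continuous data, differences between the groups will be analysed using the independent T-test", with Mann-Whitney if normality fails. Variables that differ significantly between the groups then become covariates in a regression.

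**The concern.** The aim is an association between periodontitis and coronary calcification. A risk score measures no artery: it restates age, smoking, blood pressure, lipids and, for Reynolds, CRP. If the periodontitis group is older or smokes more, its score rises with no vascular effect of periodontitis. Reynolds has a further link to the exposure, because one of its inputs is a marker that the protocol says periodontitis raises. A difference in either score could be taken as support for the aim when it reflects only the make-up of the groups.

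The covariate rule in section 9 adds a second problem. It ties adjustment to significance with 25 per group. A shared risk factor can be unbalanced and still miss significance, and so go unadjusted. In the other direction, a score that does differ could itself become a covariate. If that score is Reynolds, the model adjusts for hs-CRP, which the protocol places on the proposed pathway, and part of the association being sought could be removed.

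**Working it through.** The protocol gives no sample size calculation, alpha or expected difference for these scores, so there is no figure of its own to reproduce.

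**Step 1. Overlap of inputs (section 7.1.2 against the shared list in section 1).**

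| Score | Inputs as described | On the shared list | Not on the list |
|---|---|---|---|
| Framingham | 6 | 3: age, sex, smoking | total cholesterol, HDL, systolic pressure |
| Reynolds | 7 | 2: age, smoking | parental history, blood pressure, total cholesterol, HDL, hs-CRP |

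Counting hs-CRP as an input raised by periodontitis, 3 of the 7 Reynolds inputs are tied to the exposure.

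**Step 2. How often a score would differ with no arterial effect.** Assumptions: a score of m equally weighted, independent, standardised inputs, k of them shifted by d SD in the periodontitis group; 25 per group; two-sided 5% level; normal approximation.

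- Score shift: D = k × d / √m
- Standardised difference: z = D / √(2/25)
- P(significant) ≈ Φ(z − 1.96); P(higher mean) = Φ(z)

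Example, Framingham with d = 0.3: D = 3 × 0.3 / √6 = 0.37; z = 1.30; P(significant) = 25%; P(higher mean) = 90%.

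| Score | d | D | P(significant) | P(higher mean) |
|---|---|---|---|---|
| Framingham (k = 3, m = 6) | 0.2 | 0.24 | 14% | 81% |
| | 0.3 | 0.37 | 25% | 90% |
| | 0.5 | 0.61 | 58% | 98% |
| Reynolds with CRP (k = 3, m = 7) | 0.2 | 0.23 | 12% | 79% |
| | 0.3 | 0.34 | 22% | 89% |
| | 0.5 | 0.57 | 52% | 98% |
| Reynolds without CRP (k = 2, m = 7) | 0.2 | 0.15 | 8% | 70% |
| | 0.3 | 0.23 | 12% | 79% |
| | 0.5 | 0.38 | 27% | 91% |

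With no shift the figures are 5% and 50%.

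**Step 3. CRP alone.** The difference of 1.56 mg/l is from section 1. No SD is given, so a range is assumed. With 25 per group the chance that CRP differs significantly is 79% at SD 2, 45% at SD 3, 28% at SD 4, 20% at SD 5 and 15% at SD 6 mg/l.

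To illustrate the effect on Reynolds, assume predicted risk is log-linear in hs-CRP with a coefficient of 0.1 to 0.2 per log unit.

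- Control at 1.0 mg/l: ln(2.56/1.0) = 0.940; the risk multiplier is exp(0.094) to exp(0.188) = 1.10 to 1.21.
- Control at 2.0 mg/l: ln(3.56/2.0) = 0.577; the multiplier is 1.06 to 1.12.

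The coefficient and the control values are not in the protocol.

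**Step 4. What the covariate rule in section 9 would catch.** For a single continuous risk factor, the step 2 formula with k = m = 1 gives the chance that an imbalance of d SD reaches significance.

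- d = 0.2: z = 0.71, chance 10%
- d = 0.3: z = 1.06, chance 18%
- d = 0.5: z = 1.77, chance 42%

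Even an imbalance of half a standard deviation would go unadjusted in more than half of such studies.

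**The case against.** The strongest reply is that the protocol never presents a higher score as a sign of atherosclerosis. The heading of 7.1.2 covers parameters as well as endpoints, and the matching heading of 7.1.1 includes PISA, which is the exposure; being listed there does not make an item an outcome. The t-test sentence in section 9 is general and names neither score. The primary correlation and the EndoScore use neither. Details of adjustment may be in a statistical analysis plan that is not at hand. All of this stands, and it limits the point to interpretation and to the covariate rule, which the protocol itself states.

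A reader might go further in four ways that the documents do not support.

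- That the scores simply add up shared risk factors. By the protocol's own list the overlap is 3 of 6 inputs for Framingham and 2 of 7 for Reynolds, plus hs-CRP.
- That a difference is certain. The protocol gives no group difference in age, sex or smoking, and under the assumed shifts a significant result is far from assured.
- That the scores cannot be adjusted for age, sex or smoking. Such a regression can be fitted; what remains reflects blood pressure, lipids and, for Reynolds, parental history and CRP, which is still not a measure of the arteries.
- That hs-CRP is one more confounder. On the protocol's account it lies on the pathway, which is why adjusting for it is a problem.

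It is also fair to say that relabelling the two scores would change little by itself. The useful change is the adjusted analysis.

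**Conclusion.** The concern holds in a limited form. Both scores are predicted-risk composites that share age and smoking (and, for Framingham, sex) with periodontitis, and Reynolds also contains hs-CRP. A higher score in the periodontitis group is the expected direction without any arterial effect: 79 to 98% of studies would show a higher mean and 12 to 58% a significant difference, across Framingham and Reynolds with CRP. These figures rest on assumed shifts of 0.2 to 0.5 SD and a simplified, equally weighted score, so they show plausibility and are not a forecast. A difference in either score should not be read as evidence of an association with coronary atherosclerosis.

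The more practical weakness is in section 9. Significance-driven selection with 25 per group can leave shared risk unadjusted, or can bring Reynolds and its pathway variable into the model. The primary PISA-calcium correlation is not computed from the scores, so this is an improvement to make and not a flaw that invalidates the study.

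**What to change.** In section 9, pre-specify a supporting analysis of PISA against the coronary calcium score adjusted for the Framingham score, for example a partial Spearman correlation or a rank regression. Run it whether or not Framingham differs significantly between the groups, and state that Reynolds does not enter that model because it contains hs-CRP. A single summary score suits 50 participants. It reduces confounding but does not remove it: shared factors such as socio-economic status, stress, alcohol and overweight are not among its listed inputs.

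In section 7.1.2 or 7.1.3, describe both scores as descriptors of baseline risk, and say that group differences in them are not evidence of atherosclerosis.

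The cost is wording only. Every input is already collected under section 7.1.3. The small downside is two fewer nominal secondary endpoints.
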